### **9.4. Adverse Events (AEs) Serious Adverse Events (SAEs), and Other Safety Reporting**

#### **9.4.1. Definition of Adverse Events**

An AE is defined as any untoward medical occurrence in a participant administered a pharmaceutical product during the course of a clinical investigation. An AE can therefore be any unfavorable and unintended sign, symptom, or disease temporally associated with the use of an investigational product, whether or not thought to be related to the investigational product. In addition to new events, any increase in the severity or frequency of a pre-existing condition that occurs after the participant/parent/legal guardian/legally authorized representative signs the ICF for participation is considered an AE. This includes any side effect, injury, toxicity, or sensitivity reaction.

A suspected adverse reaction is any AE for which there is a reasonable possibility that the drug caused the AE. For the purposes of expedited safety reporting, “reasonable possibility” means there is evidence to suggest a causal relationship between the drug and the AE.

Suspected adverse reaction implies a lesser degree of certainty about causality than adverse reaction, which means any AE caused by a drug.

Life-threatening AE or life-threatening suspected adverse reaction is an AE or suspected adverse reaction that, in the view of either the Investigator or Sponsor, places the study participant at immediate risk of death. It does not include an AE or suspected adverse reaction that, had it occurred in a more severe form, might have caused death.

An AE or suspected adverse reaction is considered to be “unexpected” if it is not listed in the Reference Safety Information section of the current IB or is not listed at the specificity or severity that has been observed.

The Investigator will assess each AE for seriousness, severity, and relationship to investigational product.

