**2.2.3. Study Design**

C5351005 (OLE) is designed as a multicenter, global, open-label extension study. The primary objective is to assess the long-term safety of osivelotor in participants with SCD. This study is available to eligible participants who have previously enrolled in a Pfizer-sponsored osivelotor clinical study and meet the entry criteria for this study.

Eligible participants will receive open-label osivelotor at Baseline (Day 1). It is intended that Day 1 coincides with the final visit from the originating osivelotor study. End of Treatment (EOT) assessments from the originating study will serve as Baseline assessments for this study. If Day 1 for this study is greater than 7 days from the completion of the originating study, new baseline assessments will be obtained. If during the period between Day 1 of this study and completion of the originating study no dose is received for greater than 3 consecutive days, an appropriate loading dose will be administered prior to continued maintenance dosing.

Only participants from C5351004 Part A (also referred to as the “parent study”) were enrolled into the OLE. C5351004 Part A is a study which enrolled only adult participants. There are two sets of participants rolling over from C5351004 Part A to the OLE study – (i) participants without a delayed start (Date of first dose in C5351005 – EOT date from C5351004 + 1 ≤ 42 days) and (ii) participants with a delayed start of OLE (Date of first dose in C5351005 – EOT date from C5351004 + 1 > 42 days). Each set follows a distinct schedule of assessments as outlined in the C5351005 protocol.

**3. ENDPOINTS AND BASELINE VARIABLES: DEFINITIONS AND CONVENTIONS****3.1. Primary Endpoint(s)****3.1.1. Incidence of TEAEs**

A treatment-emergent adverse event (TEAE) is defined as an AE that occurs during the effective duration of treatment defined as the time from the first dose of study drug through last dose of study drug + 56 days.

TEAEs that occur in the parent study are not counted as TEAEs in this study. In case, the start date of AE is the same date as the treatment start date and the question in the AE CRF page “Is this AE continuing from the parent study?” = “Yes”, then the event is not a TEAE,

as long as it can be confirmed that the AE in question had a start date in the parent study and no end date in the parent study.

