In addition, in case the start date of AE is unknown (partially or fully unknown) and the response to the question in AE CRF page “If complete date is not known or the start date is the same as Day 1, did the AE start prior to dosing?” = “No”, then the event is a TEAE. This particular CRF question will only be used when the AE start date is not completely known or the start date is the same as Day 1.

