- Treatment-related TEAEs by SOC and PT
- Treatment emergent SAEs by SOC and PT
- Treatment-related treatment emergent SAEs by SOC and PT
- TEAEs leading to study discontinuation by SOC and PT
- TEAEs leading to study treatment discontinuation by SOC and PT
- TEAEs leading to study treatment interruption by SOC and PT
- TEAEs leading to dose reduction by SOC and PT
- TEAEs leading to death by SOC and PT
- Treatment emergent non-serious AEs by SOC and PT

AEs will be sorted in alphabetical order for SOC and then overall descending frequency of PTs within each SOC by all participants.

The frequency of participants who experience each TEAE or treatment-related AE will be determined as follows: A participant experiencing the same AE multiple times will only be counted once for the preferred term. Similarly, if a participant experiences multiple AEs within the same SOC, that participant will be counted only once for that system. If changes in the severity of an AE are recorded in the eCRF, only the most severe incidence of the AE will be counted. If a participant experiences multiple occurrences of a TEAE, only the most severe related event or the worst severity (analysis dependent), will be counted for each participant within each SOC or preferred term for the summaries of treatment-related AEs.

Listing of all AEs will be provided.

A separate listing of deaths, if any, will be provided.

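### The TEAE definition has no worsening clause and drops carried-over parent-study AEs without comparing severity, so whether an on-drug worsening enters the primary endpoint depends on how the site records it

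*SAP*

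**What the plan says.** TEAE incidence is the first primary endpoint. The protocol does not define the term beyond its abbreviation, so the definition rests on SAP 3.1.1:

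- The base rule is that "A treatment-emergent adverse event (TEAE) is defined as an AE that occurs during the effective duration of treatment", which runs from first extension dose to last dose plus 56 days.
- Parent-study events are set aside: "TEAEs that occur in the parent study are not counted as TEAEs in this study".
- An AE that starts on the treatment start date and has a Yes to the CRF question "Is this AE continuing from the parent study" drops out of the count on one condition: "as long as it can be confirmed that the AE in question had a start date in the parent study and no end date" there.
- If the start date is incomplete or is Day 1, the CRF asks whether the AE began before dosing, and a No makes it a TEAE. On when that question applies, the SAP says: "This particular CRF question will only be used when the AE start date is not completely known" or falls on Day 1.

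SAP 6.1.1 mentions severity change once, as a counting rule: "If changes in the severity of an AE are recorded in the eCRF, only the most severe incidence of the AE will be counted".

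Protocol 9.4.1 includes as an AE "any increase in the severity or frequency of a pre-existing condition that occurs after the participant/parent/legal guardian/legally authorized representative signs the ICF". Protocol 9.4.7.2 has a laboratory abnormality entered again when its severity, seriousness or etiology changes. SAP 6.1 says that the primary safety estimand uses all data collected from consent onward.

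**The concern.** A long-term extension is meant to find drug effects that persist and get worse with further exposure. SAP 2.2.3 says that all enrolled participants came from Part A of C5351004, and protocol 3.2.1 describes that part as open-label osivelotor treatment. Inclusion criterion 1 also admits participants who stopped parent-study drug because of an AE. Some participants can therefore be expected to enter with an AE still open. Protocol 7.5.1 treats headache, dizziness or fatigue that is new or increased from baseline as a sign of impaired oxygen offloading, so the protocol itself regards worsening as a signal.

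The TEAE rule, by contrast, tests only when an event began. Every summary in SAP 6.1.1 is built on TEAEs: overall, by maximum severity, related, serious, and leading to interruption, dose reduction, discontinuation or death. The SCD-related AE tables in SAP 6.2.3 are restricted in the same way. One missing clause therefore affects all of them.

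**Working it through.** There is no plan figure to reproduce, because neither document gives a count of AEs open at roll-over or of AEs that later worsened. The check is to apply SAP 3.1.1 to each way the same clinical course could be recorded. Take a non-laboratory AE that begins in the parent study at Grade 1, is open at roll-over, and reaches Grade 3 while the participant is on extension drug.

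| How it is recorded | Rule that applies | TEAE? |
|---|---|---|
| 1. One record with its parent-study start date; grade updated later | Onset before first dose; parent-study exclusion | No |
| 2. Re-entered on the extension CRF dated Day 1, continuing = Yes; grade updated later | Day 1 carry-over exclusion | No |
| 3. Worsening falls on Day 1, dated Day 1, continuing = Yes | Day 1 carry-over exclusion | No |
| 4. Worsening entered as a new AE starting after Day 1 | Occurs in the window; Day 1 rule does not reach it | Yes |
| 5. For comparison: a laboratory abnormality, re-entered under protocol 9.4.7.2 | As row 4, if the new entry has its own start date | Yes |

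Rows 1, 2 and 4 can describe the same patient with the same worsening, yet the answer differs. Protocol 9.4.1 would call the worsening an AE in each of them.

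Nothing elsewhere in the SAP rescues rows 1 to 3:

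- The conditions on the carry-over exclusion are a parent start date and no parent end date. Grade and seriousness are not compared.
- The severity sentence in SAP 6.1.1 selects which grade to count. It does not make an event treatment-emergent.
- SAP 5.4.1.4 says that no start-date imputation is needed to define a TEAE because of the CRF design, which again ties the classification to onset.

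**Size.** The share of participants affected is at most

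(share with an AE open at roll-over) × (share of these with a worsening in the window) × (share of the worsenings kept in the old record).

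The documents give none of the three factors. The third can lie anywhere from 0 to 100%. At 0% the product is zero; at 100% every such worsening is lost.

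**The case against.** The strongest counter-argument is textual. SAP 3.1.1 says that the AE occurs in the window, not that it starts there, and protocol 9.4.1 makes a worsening an AE in its own right. Read together, a worsening at Week 6 is an AE occurring on treatment and so a TEAE. This stands for row 4. It does not help rows 2 and 3, where the SAP says expressly that the event is not a TEAE, and it is hard to apply to row 1, where the only start date precedes first dose.

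The carry-over rule is also narrow. It applies only to AEs dated on the treatment start date, and it reads as a guard against double counting when Day 1 coincides with the parent study's last visit. That purpose is sound, but a severity check would serve it equally well.

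Other outputs limit the damage. All AEs are listed, deaths are listed separately, laboratory and vital-sign changes are summarised from baseline, and disposition gives reasons for discontinuation. The events would thus remain visible in the report, but a listing does not correct an incidence table.

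A reader might infer that every parent-study AE that worsens is missing from the primary endpoint. The documents do not support that: rows 4 and 5 are counted. Nor does SAP 6.1.1 say that severity changes stay within one record; its sentence is conditional and fits several records equally well. Protocol 11.1.7 refers to separate CRF completion guidance, which may settle the matter and is not among the documents reviewed.

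**Conclusion.** The point holds as a defect in the specification of a primary endpoint. SAP 3.1.1 excludes carried-over AEs without a severity check and has no worsening clause. A parent-study AE that increases in grade or becomes serious on extension drug is therefore absent from all TEAE tables when kept as a continuing record, and present when entered as a new AE starting after Day 1. For non-laboratory events neither document says which should happen.

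For each record kept as continuing, the loss is complete. The effect on the overall incidence cannot be computed from the documents and may be zero. The conclusion assumes only that at least some sites may keep a worsening in the carried-over record, which the continuing-from-parent question on the CRF makes possible.

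**What to change.** Revise SAP 3.1.1 in four respects:

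1. **Definition.** For example: *A TEAE is an AE with onset on or after the first OLE dose, or an AE ongoing at the first OLE dose that increases in severity grade or becomes serious, in either case no later than 56 days after the last dose.*
2. **Carry-over exclusion.** Apply it only where the grade and seriousness recorded in the extension do not exceed those of the last parent-study record.
3. **Onset of a worsening.** Use the date of worsening where it is recorded. Otherwise classify by comparing the maximum extension grade with the last parent-study grade. Say what happens to an undated worsening that may fall after the window: the end-of-study visit is about 12 weeks (84 days) after last dose, so up to about 84 − 56 = 28 days of collection lie outside it. Counting such cases as TEAEs is the cautious choice.
4. **Recording convention.** State whether a non-laboratory AE that worsens gets a new record or an update, consistent with the CRF guidance. The classification should give the same answer either way.

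The cost is SAP wording and a merge with parent-study AE grades and seriousness. SAP 3.1.1 already needs parent AE start and end dates, and SAP 3.4 already draws on the parent database, so the source is in use; grades are an addition. The documents do not show that the eCRF captures the date of a severity change, hence the fallback in item 3. TEAE incidence may rise slightly.

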#### **9.4.6. Adverse Event Reporting**

##### **9.4.6.1. General AE Reporting**

All AEs/SAEs will be recorded from the time the study participant/parent/legal guardian/legally authorized representative signs the ICF/assent form until the EOS Visit or ET Visit, whichever comes first. The AE or SAE must be recorded on the CRF and the SAE reported using PSSA. The Investigator is responsible for evaluating all AEs/SAEs, obtaining supporting documents, and ensuring that documentation of the event is complete. Details of each reported AE/SAE must include at a minimum severity, relationship to study treatment, duration, and outcome.

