#### 5. GENERAL METHODOLOGY AND CONVENTIONS

##### 5.1. Definition and Terminology

- Day 1 is the day of first dose of C5351005 study drug administration.
- EOT information is collected on the C5351005 EOT eCRF page. The EOT date from this form will serve as the last dose of study (eg for defining TEAE etc).
- Date of study completion/discontinuation is the study completion/discontinuation date from C5351005 EOS eCRF page. If this date is missing, date of last known assessment will be used.
- Study Day is defined relative to the C5351005 date of first dose of study drug, i.e., Day 1.

For study assessments or events that occur on or after the date of first dose of study drug, the study day of an assessment/event is calculated as:

Study Day = event date – date of first dose + 1.

For pre-treatment events, the study day is calculated as:

Study Day = event date – date of first dose.

- Study Visit is the nominal visit as recorded on the CRF.
- Visit windows rules are defined in Appendix 1. No windowing rules will be applied to PK endpoints where only nominal visits will be used for presentation purposes.
- Treatment of Outliers for Pharmacokinetic Data

Individual blood and plasma concentration-time points, if considered anomalous, may be excluded from the analysis at the discretion of the pharmacokineticist following a review of the available documentation.

Entire individual treatment profiles for any participant, if considered anomalous, may be excluded following review of the available documentation and discussion with the Sponsor. However, results of analysis with and without the excluded profiles may be presented in the CSR.

Any such exclusion or treatment of anomalous PK data, as described above, will be discussed with the Sponsor's Clinical Pharmacologist and clearly described in the CSR along with justification for exclusion.

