#### 5.4.1.4. Start Dates for Adverse Events

For this study, there is no need for imputation of start dates of AE to define TEAE and to determine if the AE occurs prior to dosing based on the CRF design.

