#### 5.4.1.5. Stop Dates for Adverse Events

AE stop dates will not be imputed.

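### An AE with an incomplete start date and the CRF answer 'No' becomes a TEAE without any check against the last dose + 56 days limit, even when its known month lies wholly after that limit

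*SAP*

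**What the plan says.** SAP 3.1.1 defines the TEAE period as "the time from the first dose of study drug through last dose of study drug + 56 days". SAP 5.1 fixes the end point: "The EOT date from this form will serve as the last dose of study".

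The same section then adds a rule "in case the start date of AE is unknown (partially or fully unknown"). It turns on a CRF question that asks, where the complete date is not known or is Day 1, "did the AE start prior to dosing". If the answer is 'No', the SAP concludes "then the event is a TEAE. This particular CRF question will only be used when the AE start date is not completely known" or when the start date is Day 1.

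On missing dates, SAP 5.4.1.4 says that, given the CRF design, "there is no need for imputation of start dates of AE to define TEAE" or to decide whether the AE preceded dosing. SAP 5.4.1.5 adds that "AE stop dates will not be imputed".

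AE recording runs past Day 56. Protocol 9.4.6.1 has AEs recorded "until the EOS Visit or ET Visit, whichever comes first". Protocol 5.1 puts the EOS visit about 12 weeks after last dose, and Protocol 9.4.7 sets active collection at no less than 63 days after last dose.

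**The concern.** The TEAE period has two ends, but the rule for incomplete dates tests only the first. An AE that began after treatment stopped will naturally be answered 'No', and the rule then makes it a TEAE. Neither 3.1.1 nor 5.4.1 compares the known month or year with last dose + 56 days.

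An event that cannot have started inside the period is therefore counted if its day was left blank and excluded if the day was entered. TEAE incidence is a primary endpoint. The same flag feeds the serious, fatal and treatment-related tables in SAP 6.1.1 and the SCD-related tables in SAP 6.2.3. These are split by dose and by delayed start (SAP 5.3), so a single event can show in a small column.

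**Working it through.** The plan states no figure on this point, so there is none to reproduce. The check has four steps.

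**1. Can such AEs be in the database?**
- TEAE limit: last dose + 56 days (SAP 3.1.1).
- Collection to an EOS visit at 12 weeks: 84 − 56 = 28 days beyond the limit (Protocol 5.1 and 9.4.6.1).
- Collection to the stated minimum only: 63 − 56 = 7 days beyond the limit (Protocol 9.4.7).

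So they can, over a span of about 7 to 28 days. An early ET visit can shorten it.

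**2. A worked case.** Take a last dose on 10 Jan 2025. The limit is 10 Jan + 56 days = 7 Mar 2025, and Day 84 is 4 Apr 2025. An AE dated 1 Apr 2025 is on Day 81 and is not a TEAE. If it is recorded as Apr 2025 and answered 'No', it is a TEAE, although every day in April is after the limit.

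**3. How often does the month alone prove lateness?** Assume last-dose dates spread evenly over a 365-day year, and onset spread evenly from Day 57 to the end of collection. An AE starting on Day 56 + j is provably late if the first day of its month falls after the limit. For each j up to 28 that holds for j last-dose dates per month boundary, or 12j per year.
- Collection to Day 84: 12 × (1 + 2 + … + 28) = 12 × 406 = 4,872 of 365 × 28 = 10,220 combinations, or 47.7%.
- Collection to Day 63: 12 × (1 + 2 + … + 7) = 12 × 28 = 336 of 365 × 7 = 2,555 combinations, or 13.2%.

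A direct count over all 2025 last-dose dates gives the same numbers. These shares apply only to AEs starting after Day 56, dated by month and year, and answered 'No'.

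**4. What could this do to the endpoint?** Two inputs are not in the documents and are assumed: f, the share of AEs with an incomplete start date (2% to 20%), and D, the days on treatment (84 to 504). With a constant AE rate,

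extra TEAE events ÷ TEAEs under the 56-day rule = f × (days beyond the limit) ÷ (D + 56).

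| D (days) | Collection to Day 84 (28 extra days) | Collection to Day 63 (7 extra days) |
|---|---|---|
| 84 | f × 28/140 = 0.4% to 4.0% | f × 7/140 = 0.1% to 1.0% |
| 252 | f × 28/308 = 0.18% to 1.8% | f × 7/308 = 0.05% to 0.45% |
| 504 | f × 28/560 = 0.1% to 1.0% | f × 7/560 = 0.03% to 0.25% |

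For participant-level incidence, use 1 − exp(−rate × period), adding f × 28 days to the period. With 0.5 to 4 AEs per year, f of 5% to 20% and D of 84 to 252, incidence rises by about 0.05 to 1.4 percentage points. The largest case is 2 AEs per year, D = 84 and f = 20%: 53.5% becomes 54.9%.

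These figures count every incompletely dated AE after the limit. The provably late ones are a subset. If all incomplete dates were month-and-year only, the 4.0% upper figure would contain 4.0% × 0.477 = 1.9% provably late.

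**The case against.** The strongest reply is that the general definition still governs. The incomplete-date rule opens as an addition to it and concerns onset before dosing, so a programmer could apply both and drop an AE whose month is wholly after the limit. That reading is possible. But the rule ends in an unconditional classification and gives no way to test a partial date against the upper limit, so the literal text favours counting the event.

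A second reply is that counting uncertain dates is cautious for a safety endpoint. That stands for ambiguous dates. An AE whose earliest possible start is after the limit is not uncertain.

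A third is that little is at stake. No hypothesis is tested, and all AEs are listed, with partial dates shown unimputed, so affected events can be found. The primary estimand also takes in all safety data after consent. This stands as to size. The estimand wording does not settle which AEs are TEAEs, since 3.1.1 does that.

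A reader might go further in three ways that the documents do not support:
- *Every incompletely dated AE becomes a TEAE, with no end in time.* The rule needs the answer 'No', and AE recording itself stops at the EOS or ET visit.
- *SAP 5.4.1.4 is wrong.* It says only that imputation is not needed. Comparing the known month with a limit imputes nothing, so the statement can stand.
- *A third of follow-up is exposed.* The fraction 28/84 covers only the time after last dose. Against treatment time plus 56 days, the extra 28 days are 5% (D = 504) to 20% (D = 84), and only for incompletely dated AEs.

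**Conclusion.** The gap in the text is real and minor. As written, SAP 3.1.1 counts as treatment-emergent an AE that its own known month shows to be outside the TEAE period, provided the CRF answer is 'No'. The error can only add TEAEs.

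The 13% to 48% range rests on evenly spread last-dose and onset dates. It describes how many late, month-only AEs can be recognised as late, not an effect on the endpoint. The endpoint effect cannot be fixed without the share of incomplete dates. Over the assumed ranges, extra TEAE events stay at or below 4% of the total, and few are expected. The point does not question the choice of 56 days.

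**What to change.** - **SAP 3.1.1:** state that an AE with an incomplete start date and the answer 'No' is a TEAE unless its earliest possible start date, taken from the known date parts, is after last dose + 56 days, or whatever limit is kept. Ambiguous and fully unknown dates remain TEAEs.
- **SAP 5.4.1.4:** keep the no-imputation statement and add a cross-reference to this check.

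The cost is two sentences and one line of derivation code, with no new data. Some dependence on date completeness remains: under the Day 84 assumptions, about 52% (100% − 47.7%) of month-only AEs starting on Days 57 to 84 would still count as TEAEs, although the same events fully dated would not.
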